Main in- and exclusion criteria	
Main inclusion criteria (for a complete list see Section 3.3.2):
 
 • Patients who have completed treatment in the parent HS spesolimab trial (1368-0052) without premature discontinuation. 
Main exclusion criteria (for a complete list see Section 3.3.3):
 
 • Patients who experienced study treatment-limiting adverse events during the 1368-0052 parent trial. • Use of any restricted medication or any drug considered by the investigator likely to interfere with the safe conduct of the study since the last visit of the 1368-0052 parent trial. • Any condition which in the opinion of the investigator affects the safety of the patient, the patient's ability to participate in this trial or could compromise the quality of data.
Test product(s)	Spesolimab
dose	At Visit 1 patients from the placebo group in the parent 1368-0052 trial are given [REDACTED] of spesolimab plus [REDACTED] placebo followed by [REDACTED] spesolimab every [REDACTED] weeks. At Visit 1 patients from the active group in the parent 1368-0052 trial are given infusion of placebo plus [REDACTED] spesolimab followed by [REDACTED] spesolimab every [REDACTED] weeks. Administration of study medication at Visit 1 is blinded. Refer to Section 4.1.2 for details. At Week 12, all patients will be assessed for total number of ANs and DF and HS PGA. Based on the individual responder status at baseline, decisions on further dosing will be taken as depicted in Table 3.1: 1 .
mode of administration	[REDACTED] at Visit 1 only, and s.c. at all visits
Duration of treatment	[REDACTED] weeks
Statistical methods	Given the single arm and open-label nature of this trial, no hypothesis testing will be performed in the confirmatory sense. All statistical assessments will be performed in an explorative manner to better understand the efficacy and safety profile of spesolimab.

FLOW CHART – UP TO W12

Trial Periods							
Visit	1*	2	3	4	5	6	7
Week (W)	W0	W1	W2	W3	W4	W5	W6
Day							
Time Window for Visits	n/a	±2 days	±2 days	±2 days	±2 days	±2 days	±2 days
Informed consent	X						
Demographics	X						
Medical history	X						
Columbia-Suicide Severity Rating Scale (C-SSRS)	X	X	X	X	X	X	X
Physical examination ¹ -Complete (C) or Targeted (T)	C	T	T	T	T	T	T
Height	X						
Weight	X		X		X		X
Vital Signs ²	X ^{2a}	X ^{2b}	X ^{2b}	X	X	X	X
Safety Laboratory tests (blood and urine) ³	X		X		X		X
Infection Testing ⁴	X						

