Trial Periods	Maintenance Treatment Period (visits every 2 weeks)	End of Treatment**	Follow-up 1 (2 weeks after last dose)	End of Study (16 weeks after last dose)
Visit	8 to 52	EoT	FUP1	EoS ¹⁵
Day				
Week (W)				
Time window for visits	±3 days	±3 days	±3 days	+10 days
IRT contact	X	X		
Concomitant therapy	X	X	X	X
Columbia-Suicide Severity Rating Scale (C-SSRS)	X	X	X	X
Physical examination ¹⁰	Targeted	Targeted	Complete	Targeted
Vital signs ¹¹	X	X	X	X
Weight	Every second visit	X	X	X
Safety Laboratory tests (blood and urine) ¹²	Every second visit	X	X	X
Pregnancy testing ¹³	X	X	X	X
Infection testing ¹⁴	X ¹⁴	X ¹⁴		
Local tolerability assessment	X	X		
All AEs/SAEs/AESIs ¹⁵	X	X	X	X ¹⁵
Pain NRS	Every second visit	X	X	
DLQI, PGI-S, PGI-C, HiSQOL ¹⁶	Every second visit	X	X	
FACIT Fatigue Scale ¹⁶	Every second visit	X	X	
HiSCR, HS-PGA, IHS4, HASI ¹⁷	X ¹⁷	X	X	
Abscess count. Inflammatory nodule count. Non-inflammatory nodule count. Draining Fistula count. ¹⁷	X ¹⁷	X	X	
Photography ¹⁸	X ¹⁸	X	X	
ADA/Nab ¹⁹	X ¹⁹	X	X ²²	X
PK Sampling ¹⁹	X ¹⁹	X	X ²²	X
hs-CRP ²⁰	X ²⁰	X		
12 lead-ECG (local) ²¹	X ²¹	X	X	X
Administer study drug (every 2 weeks)	X	X		

[figure not shown]
**Patients who discontinue trial treatment prematurely should undergo the EoT visit as soon as possible, the Follow-up (FUP 1) visit two weeks after last dose, and the EoS visit 16 weeks after the last dose. If a patient discontinues the study during a scheduled treatment visit then the visit is considered an EoT visit.

***Week █ Patients identified as a Non-responder AND up-titrated to █ at Week █ must undergo a re-assessment of their HS-PGA. If there is no change or no improvement in their HS-PGA grade at Week █ compared to Week █ then the patient MUST be discontinued from the trial (Table 3.1: 1). The HS-PGA page and Abscess and Inflammatory Nodule count page are added as “unscheduled visits” at Week █ to document the re-assessment. This assessment is recommended to be performed at the start of the visit. If the patient is discontinued at the Week █ visit, then this visit can be considered the EoT visit.

Every second visit = every other visit starting from W14.

10. Complete physical examination includes general appearance as well as evaluation of all organ systems; Targeted physical examination includes evaluation of organ systems associated with AE(s) symptoms or laboratory abnormalities.

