3. DESCRIPTION OF DESIGN AND TRIAL POPULATION

3.1 OVERALL TRIAL DESIGN

This open label, single-arm, multi-regimen, 2-year extension study investigates the long-term safety and efficacy of spesolimab in patients with HS who have completed their treatment in the 1368-0052 PoCC trial. BI trial 1368-0052 is the first trial from which patients will rollover into this extension trial. Patients rolling over into this trial must have completed the treatment period as required in the 1368-0052 PoCC trial. Ideally, the end of treatment (EoT) visit of the preceding trial is the baseline visit (V1) of this extension trial.

This extension trial consists of a [REDACTED] weeks treatment period followed by a [REDACTED] week safety follow-up period.

Approximately [REDACTED] patients from the 1368-0052 PoCC trial are planned to be rolled over into this open-label extension study.

Patients from the placebo arm of the 1368-0052 PoCC trial will be given an initial [REDACTED] dose of spesolimab plus [REDACTED] placebo, followed by [REDACTED] spesolimab [REDACTED] every [REDACTED] weeks [REDACTED]). Patients from the active arm of the 1368-0052 PoCC trial will be given an initial [REDACTED] placebo plus [REDACTED] spesolimab [REDACTED], followed by [REDACTED] spesolimab [REDACTED] every [REDACTED]. Administration of trial medication at Visit 1 is blinded. See [Section 3.1.1](#) for more details.

[figure not shown]
At Week [REDACTED] of this extension trial, all patients will be assessed for the change of HS-PGA grade. The change in HS-PGA grade will be compared with the assessment at baseline of this extension trial / Week [REDACTED] of the 1368-0052 PoCC trial. Based on the individual responder status decisions on further dosing will be taken as depicted in [Table 3.1: 1](#).

Table 3.1: 1 Week 12 Dose Modification Management

Baseline	Assessment at Week 12	Management
Status from Week 12 of 1368-0052 PoCC trial	HS-PGA grade change from baseline HS-PGA grade of this trial	
Responder (Achieved HiSCR 50)	No change or improvement in grade (i.e., reduction by at least 1 grade)	Continue the same dose
	Worsening in grade (i.e., increase by at least 1 grade)	Option to increase the dose to [REDACTED]
Partial Responder (Achieved HiSCR 25 but did not achieve HiSCR 50)	Improvement in grade	Continue the same dose
	No change or worsening in grade	Increase the dose to [REDACTED]
Non-responder (Did not achieve HiSCR 25)	Improvement in grade	Continue the same dose

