	No change or worsening in grade	Increase the dose to [REDACTED] Re-assess HS-PGA grade at week [REDACTED] and discontinue, if no change or worsening observed compared to Week [REDACTED]

Responder is defined as achievement of HiSCR 50 in the 1368-0052 PoCC trial, partial responders are defined as patients who did not achieve HiSCR 50, but achieved at least a [REDACTED] in AN count relative to baseline in the 1368-0052 PoCC trial, and non-responders are defined as patients who have shown less than [REDACTED] in AN counts or have worsening of the disease in the 1368-0052 PoCC trial.

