4.1.2 Selection of doses in the trial and dose modifications

In the 1368-0052 PoCC trial, a fixed rather than weight-based dose regimen was selected. Early trials of therapeutic monoclonal antibodies often investigate bodyweight-based regimens to reduce the inter-subject variability in drug exposure. However, there is generally only a modest contribution of body weight to the overall PK and PD variability of monoclonal antibodies. Furthermore, monoclonal antibodies are highly target specific and offer a relatively large therapeutic window compared to new chemical entities. Therefore, most monoclonal antibodies are approved at fixed doses in antibody/target excess in order to cover target turnover and maximize efficacy [R10-6267; R13-4749; R13-4753; R13-4750; R13-4754].

In this extension trial, patients from the active arm in the parent trial will be given [REDACTED] every [REDACTED], which is half the dose of the 1368-0052 PoCC trial. This is to evaluate whether these patients would be able to sustain efficacy at a lower dose. Patients who were in the placebo arm will be given a [REDACTED] dose of spesolimab, followed by [REDACTED] every [REDACTED]. The rationale is to give an opportunity to the patients from the placebo arm to be given active treatment and also to understand induction response after a placebo period. Additionally, this dose was also selected to evaluate efficacy of [REDACTED] dose. All the patients will be reassessed at Week [REDACTED] to evaluate the response and will have the option of either continuing the same dose or increasing the dose.

Data from the 1368-0052 PoCC trial will not be available prior to the 1st patient rolling over into this extension trial. When new data from the PoCC trial becomes available, the impact for this extension trial will be evaluated and if needed the dose would then be adjusted by amending this protocol.

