In case of safety concerns, e.g., due to infusion reactions, it is in the discretion of the investigator or his/her designee to adapt the infusion scheme, including but not limited to slowing down the infusion rate, interrupting the infusion and - provided no further safety concern exist - restarting at a slower rate. Further, based on his/her medical judgment he/she will provide medications such as steroids, etc., as needed (see [Section 4.2.1](#) for handling of infusion reactions). Detailed instructions for handling of infusion reactions are also provided in the “Instructions for Pharmacist” document in the ISF.

Dose modifications or adjustments are not permitted. In exceptional cases of missed or delayed visits, if any of these visits has to be rescheduled, the date of subsequent visit should be calculated from Visit 1. After Visit 3, in case of delayed visits, IMP can be administered with a minimum interval of 7 days from the next dose, only after discussion and approval from the sponsor.

Trial treatment may be restarted after a temporary reason for treatment discontinuation on a case by case basis and after consultation with the sponsor. (See [Section 3.3.4.1](#).)

During the COVID-19 pandemic, physical visits to the sites may need to be restricted to ensure patient safety. Based on a thorough assessment of the benefits and risks, the investigator may still decide to continue the trial treatment and trial medication may be administered at the patient’s home if acceptable according to local law and regulations.

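### Section 4.1.2 makes the Week 12 dose increase an option for every patient, which contradicts Table 3.1: 1; a site that follows it can leave a Non-responder outside the mandatory Week 24 stop

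*Protocol*

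**What the plan says.** **Table 3.1: 1 (Protocol 3.1)** combines responder status from the parent trial with the change in HS-PGA grade at Week 12. For a Responder who worsens the entry begins "Option to increase the dose to". For a Partial Responder ("Achieved HiSCR 25 but did not achieve HiSCR 50") or a Non-responder with no change or worsening, the increase is an instruction with no option attached. The Non-responder row adds: "Re-assess HS-PGA grade at week [REDACTED] and discontinue, if no change or worsening observed compared to Week" (week numbers blacked out). All other patients continue the same dose.

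**Section 4.1.2**, whose heading covers dose modifications, says that all patients will be reassessed and "will have the option of either continuing the same dose or increasing the dose". That sentence does not refer to the table.

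**Section 4.1.4** first says that the dose stays the same unless an increase is required, and refers to Table 3.1: 1. Later it says: "Dose modifications or adjustments are not permitted".

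**The Week 24 stop** appears in two further places. The flow chart footnote for the period from Week 14 limits it to "Patients identified as a Non-responder AND up-titrated to" the higher dose. Section 3.3.4.1 limits it to a Non-responder on 1200 mg whose HS-PGA grade has not improved between Week 12 and Week 24.

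**The synopsis** says "At Week 12, all patients will be assessed for total number of ANs and DF and HS PGA", then sends the dosing decision to Table 3.1: 1.

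**The concern.** A site can find three descriptions of one decision: a rule by patient category, an option open to everybody, and a ban. The option is the one that matters most. It removes the obligation to increase where the table imposes it, and it opens an increase to patients for whom the table offers none.

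Two things depend on this. The first is the Week 24 stop, which is triggered by having been up-titrated. Section 1.4.1 presents the response-based management as a way to limit exposure in patients who no longer benefit, and a Non-responder who was never up-titrated is outside that mandatory check. The second is the reporting. SAP 6.1 splits each prior-treatment group by up-titration, SAP 7 counts Week 12 dose modifications and Week 24 discontinuations, and SAP 7.6.3 summarises HS-PGA change by responder status. If sites apply different texts, part of what these tables show is site reading and not response to the drug.

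**Working it through.** The plan gives no figure to reproduce here, and no sample-size or power calculation is involved. The check is a comparison of texts. The week in Section 4.1.2 is blacked out; I take it as Week 12, from the title of Table 3.1: 1 and from Section 1.4.1. I take the 1200 mg in Section 3.3.4.1 to be the increased dose, because the flow chart footnote and the table attach the same stop to up-titrated Non-responders.

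**Step 1. Cross three responder statuses with three HS-PGA outcomes: 3 × 3 = 9 cells.**

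| Status | HS-PGA at Week 12 | Table 3.1: 1 | Section 4.1.2 | Ban in 4.1.4, read literally |
|---|---|---|---|---|
| Responder | improved | same dose | option | no change |
| Responder | unchanged | same dose | option | no change |
| Responder | worsened | option | option | no change |
| Partial Responder | improved | same dose | option | no change |
| Partial Responder | unchanged | increase | option | no change |
| Partial Responder | worsened | increase | option | no change |
| Non-responder | improved | same dose | option | no change |
| Non-responder | unchanged | increase | option | no change |
| Non-responder | worsened | increase | option | no change |

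Table 3.1: 1 has 4 directed increases, 1 option and 4 same-dose cells (4 + 1 + 4 = 9). Section 4.1.2 has 9 options. The two agree in 1 cell and differ in 9 − 1 = 8. The literal ban differs from the table wherever an increase is possible: 4 + 1 = 5 cells.

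**Step 2. Reach of the Week 24 stop.** Two cells matter: Non-responder unchanged and Non-responder worsened. Under the table both are up-titrated, so both meet the flow chart condition and the Section 3.3.4.1 condition, and the stop reaches 2 of 2. If a site uses the Section 4.1.2 option and keeps the dose, neither condition is met and the stop reaches 0 of 2.

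**Step 3. Does the schedule close the gap?** It does not. Flow chart footnote 17 places physician assessments at Weeks 14, 18, 22, 26, 30, 34 and 38, then every 12 weeks. Week 24 is not among them. The flow chart adds the re-assessment through unscheduled pages, for up-titrated Non-responders.

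**Step 4. Illustration.** Take two Non-responders whose HS-PGA grade is unchanged at Week 12 and again at Week 24. The one escalated under the table must stop at Week 24. The one kept on the same dose under Section 4.1.2 meets no mandatory response-based stop and could continue to the end of the 2-year treatment period unless the investigator decides otherwise.

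**Step 5. AN and DF counts.** The table has no Week 12 criterion based on AN or DF count. Adding those assessments, as the synopsis does, changes 0 of 9 cells.

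**The case against.** The strongest reply is that there is one working rule and everyone is pointed to it. The synopsis, both flow chart footnotes, Section 3.1, the design diagram, the product table, Section 4.1.4 and the SAP all refer to Table 3.1: 1, and Amendment 1 aligned the flow charts and Section 3.3.4.1 with it. The Section 4.1.2 sentence closes a paragraph on dose rationale and gives no criteria, so a site would need the table in any case. Medication is assigned through IRT, and investigators may discontinue a patient at any time on clinical judgement.

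Much of this stands, and it makes divergence less likely. It does not remove the conflict. No passage says that the table prevails over Section 4.1.2. That section carries dose modifications in its heading, and the dose entry of the synopsis refers to it for details. The documents do not describe any IRT escalation logic. Discretion to discontinue is not a stop rule.

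Three stronger readings are tempting, and the documents do not support them:

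- **That the synopsis sets a second decision rule using AN and DF counts.** It lists what is assessed, then refers the decision to Table 3.1: 1, which uses HS-PGA change at Week 12.
- **That Section 4.1.4 forbids the Week 12 increase.** The section excepts that increase beforehand, and the ban sits between text on infusion adaptation and text on delayed visits. It can be read as covering other changes. The literal clash remains, because the table's own title calls the increase a dose modification.
- **That Non-responders escape the Week 24 stop under the protocol in general.** They do so only if a site departs from the table.

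**Conclusion.** The contradiction between Section 4.1.2 and Table 3.1: 1 is real: they differ in 8 of 9 cells. The unqualified ban in Section 4.1.4 is a lesser clash, softened by the exception earlier in that section. The gap at Week 24 is conditional: it needs a site to use the Section 4.1.2 option for a Non-responder without improvement.

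The number of such patients is not given. The approximate maximum of 45 roll-over patients in Section 3.3 bounds it but does not estimate it, so a reader should not infer that all 45 are exposed to the gap. Whether sites would in fact diverge cannot be judged from the documents.

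The trial is descriptive and tests no hypothesis, so no error rate is affected. What is affected is the meaning of the up-titration groups and of the Week 24 discontinuation count, and the consistency of a mandatory stopping rule. The point is worth correcting, at the level of an internal inconsistency. The passages must be reconciled; this review takes no position on which dosing or stopping rule is right.

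**What to change.** The sponsor should reconcile Section 4.1.2, Section 4.1.4, Table 3.1: 1, the Week 24 flow chart footnote and Section 3.3.4.1:

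1. State the Week 12 rule once, saying for each category whether an increase is required, optional or not offered.
2. Replace the Section 4.1.2 sentence with a cross-reference to that statement.
3. Limit the ban in Section 4.1.4 to changes other than the Week 12 rule.
4. State whether the Week 24 re-assessment applies to a Non-responder without improvement who was not up-titrated, and use the same condition in the flow chart and Section 3.3.4.1.
5. In the same edit, align the synopsis wording on AN and DF counts with the assessment named in Section 3.1.

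The content of each rule is for the sponsor to decide. The cost is wording in a handful of protocol passages. Reconciling the text needs no new data or visits. Only if the sponsor decides under item 4 to extend the re-assessment would the added Week 24 pages also be completed for those patients.

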4.1.3 Method of assigning patients to treatment groups

An Interactive Response Technology (IRT) system will be used in this trial in order to dispense medication kits as well as manage initial/re-supply ordering of medication kits. The study site will be required to complete the appropriate module within the IRT system. The investigator will receive all necessary instructions to access the IRT system from the sponsor or chosen provider. Detailed IRT transactions and procedures will be documented in the user requirement specifications mutually agreed to by the sponsor and the IRT provider. All medication kit assignments will occur in an open label fashion except for medications provided for Visit 1. Note that the medication number is different from the patient number.

4.1.4 Drug assignment and administration of doses for each patient

Patients will be treated with spesolimab as indicated in the [Flow Chart](#) and [Section 3.1.1](#). The medication will be assigned via IRT.

At Visit 1 patients who were in the placebo arm of the 1368-0052 PoCC trial will be given an initial [REDACTED] dose of spesolimab plus [REDACTED] placebo. Patients from the active arm of the 1368-0052 PoCC trial will be given [REDACTED] placebo plus [REDACTED] spesolimab [REDACTED]

Detailed instructions for the preparation of the solution for infusion, the volume to be administered and the infusion rate as well as detailed instructions for use and handling of spesolimab syringes are provided in the ISF.

At all other visits all patients will receive [REDACTED] spesolimab [REDACTED] for the remainder of the trial unless an increase in dose to [REDACTED] is required at Week [REDACTED]. Refer to [Table 3.1: 1](#).

Patients have to be closely monitored for local or systemic hypersensitivity reactions for one hour following [REDACTED] or [REDACTED] study drug administration. Patients should be closely monitored for signs and symptoms of injection site or systemic hypersensitivity reactions following study drug administration. Injection site should not be close to a vein and it should avoid sites where the skin is tender, bruised, erythematous, or indurated, and should be alternated to other areas for subsequent doses. Study personnel should observe the injection site for signs

of redness, swelling or hardness. They should also ask patients about itching, dizziness or shortness of breath. Patients should be advised that if they experience redness, swelling or other changes at the injection site, they should notify site personnel. They should further be advised that if they experience itching all over or a feeling of being swollen, dizzy or short of breath, they should seek emergency medical attention immediately and notify site personnel.

The administration of the trial medication on all applicable study days will be done under supervision of the investigating physician or a designee at the site. If available, a pharmacist should prepare the study medication. The so-called four eye principle (two-person rule) should be applied for preparation (e.g. choosing the correct vials with the correct medication number) and administration of trial medication.

In case of safety concerns, e.g., due to infusion reactions, it is in the discretion of the investigator or his/her designee to adapt the infusion scheme, including but not limited to slowing down the infusion rate, interrupting the infusion and - provided no further safety concern exist - restarting at a slower rate. Further, based on his/her medical judgment he/she will provide medications such as steroids, etc., as needed (see [Section 4.2.1](#) for handling of infusion reactions). Detailed instructions for handling of infusion reactions are also provided in the “Instructions for Pharmacist” document in the ISF.

Dose modifications or adjustments are not permitted. In exceptional cases of missed or delayed visits, if any of these visits has to be rescheduled, the date of subsequent visit should be calculated from Visit 1. After Visit 3, in case of delayed visits, IMP can be administered with a minimum interval of 7 days from the next dose, only after discussion and approval from the sponsor.

Trial treatment may be restarted after a temporary reason for treatment discontinuation on a case by case basis and after consultation with the sponsor. (See [Section 3.3.4.1](#).)

During the COVID-19 pandemic, physical visits to the sites may need to be restricted to ensure patient safety. Based on a thorough assessment of the benefits and risks, the investigator may still decide to continue the trial treatment and trial medication may be administered at the patient’s home if acceptable according to local law and regulations.

